Detailed Protocol

Title: Effects of cannabidiol on responses to emotional stimuli (“Effects of drugs on mood and behavior” on the consent form)

P.I.: [name]

Co-Investigators: [name], [name], [name]

May 11, 2016

Objectives: To study the effects of cannabidiol (CBD), a constituent of marijuana, on responses to emotional stimuli in healthy young adults.

Aim 1. We will assess the effects of CBD on subjective and psychophysiological responses to images with positive (rewarding) vs. negative (aversive) emotional content. Our working hypothesis is that CBD will reduce subjective and psychophysiological responses to negative images without affecting responses to positive images.

Aim 2. We will examine the effect of CBD on responses to the socially rewarding and aversive information conveyed by emotional facial expressions. We will measure speed of identification for positive (rewarding) and negative (aversive) emotional expressions as they dynamically develop, psychophysiological reactions to emotional expressions and direction of attention to emotional expressions. Our working hypothesis is that CBD will slow identification of negative expressions, reduce psychophysiological responses to negative expressions, and reduce direction of attention to negative expressions without affecting responses to positive expressions.

Aim 3. We will examine the effect of cannabidiol on a controlled social interaction with a research assistant. Our working hypothesis is that the reduction in responses to negative emotional and social stimuli produced by CBD will result in greater talkativeness in a controlled social interaction.

Exploratory Aim. We will additionally measure the effects of CBD on subjective mood, including anxiety, euphoria and sedation, to determine whether the CBD’s effects on responses to emotional stimuli are mediated by effects on subjective mood, or occur above and beyond CBD-induced changes in mood.

Significance

The purpose of this project is to investigate the effects of cannabidiol (CBD) on responses to emotional stimuli in humans. CBD is one of the primary constituents in whole plant marijuana (Ashton 2001). Such cannabinoid compounds are of interest for two reasons. First, understanding the effects of these compounds may shed light on the phenomena of marijuana use and abuse. Second, studying the effects of cannabinoids may be informative about the purposes and functioning of the brain’s endocannabinoid

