In a four-session within-subjects study we will compare a placebo control to 300, 600 and 900mg of cannabidiol. In Aim 1 we will explore how cannabidiol affects reactions to rewarding vs. aversive pictures. Participants will view pleasant pictures (e.g. of parties, pets, sunsets), neutral pictures (e.g. of household objects, neutral landscapes) and unpleasant pictures (e.g. medical imagery, war scenes and disgusting objects) drawn from the standardized International Affective Picture Set (IAPS) while we measure subjective responses to these pictures using self-reports. We predict that cannabidiol will reduce subjective and psychophysiological responses to negative pictures without affecting responses to positive pictures. In Aim 2 we will examine responses to emotional facial expressions, which are an ecologically relevant category of rewarding and aversive stimuli. We will measure how quickly individuals are able to perceive happy vs. negative facial expressions using dynamically developing expressions of happiness, fear, anger and sadness. We predict that cannabidiol will blunt perception of, psychophysiological responses to and attentional bias towards negative facial expressions without affecting responses to positive facial expressions. In Aim 3 we will examine the relationship of responses to emotional stimuli with talkativeness in a controlled social interaction. We predict that cannabidiol will increase talkativeness, and this effect will be mediated by the decreased responses to negative social and emotional stimuli measured in the previous aims. Finally, on an exploratory basis we will measure the subjective effects of cannabidiol, and specifically the its effects on anxiety, sedation and euphoria, with the aim of determining whether CBD's effects on responses to emotional stimuli are related to, or independent of, its subjective effects.

Methods:

Design: The study will use a 4-session within-subjects double-blind design in which participants will receive three doses (300, 600mg and 900mg oral) of cannabidiol and a placebo in randomized order. All screening, orientation, and study session procedures

will take place in the Human Behavioral Pharmacology Laboratory suite in the L4 wing of [name]

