ABT: We hypothesize that participants will show reduced attentional bias to negative facial expressions (anger, sadness and fear) on CBD, as measured by increased reaction times for probe response for negative faces, without any change in responses to happy faces. We will conduct a Generalized Mixed Linear Model analysis in R using lme4 on the binomial variable of initial gaze direction with Drug (0, 300, 600 and 900mg) and expression type (happy, angry, fearful, sad) as independent variables, and including random variables for Subject and Drug. We will conduct a Mixed Linear Model analysis in R using lme4 on total dwell time on each face, using Drug (0, 300, 600 and 900mg) and expression type (happy, angry, fearful, sad) as independent variables, and including random variables for Subject and Drug.

IST: We hypothesize that participants will show increased talkativeness on the IST, as measured by total word count and further, that this increased talkativeness will be mediated by reduced negative responses to negative emotional and social cues (as measured in the IAPS, DEIT and ABT). We will first derive per-participant estimates of the effect of drug on responses to negative stimuli from the Mixed Linear Model analyses described above. We will then conduct a Mixed Linear Model analysis in R using lme4 on total word count with Drug (0, 300, 600 and 900mg) as an independent variable, and including random variables for Subject and Drug (per Wardle et al. 2012b). Following criteria for within-subject mediation (Judd et al. 2001), we will first establish whether drug has the hypothesized effect on talkativeness. We will then include the per-participant estimates of the effect of drug on responses to negative stimuli as covariates, and examine 1. Whether changes in responses to negative stimuli account for a significant proportion of changes in talkativeness, and 2. Whether the effect of drug on talkativeness is still significant after inclusion of the changes in responses to negative stimuli. If the effect of drug on effort is wholly mediated by changes in responses to negative stimuli, we would expect the effect of drug on talkativeness to no longer be

significant after including drug-induced changes in responses to negative stimuli as a covariate (see Wardle and de Wit 2012 for an example of this type of analysis).

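### No planned model includes session number: a session trend costs power on the dose contrasts, and trends in both mediator and word count can create or hide the Aim 3 mediation.

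*Combined protocol and SAP*

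**What the plan says.** Every model is written out under Data Analysis. IAPS, DEIT and both ABT models have Drug and stimulus type as fixed effects, with random terms for Subject and Drug (plus Actor for DEIT). The IST model is fitted "on total word count with Drug (0, 300, 600 and 900mg) as an independent variable, and including random variables for Subject and Drug". Session, period and sequence appear in none of them.

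Mediation is built on these models: "We will first derive per-participant estimates of the effect of drug on responses to negative stimuli from the Mixed Linear Model analyses described above". The plan sets a gate: "we will first establish whether drug has the hypothesized effect on talkativeness". It continues: "We will then include the per-participant estimates of the effect of drug on responses to negative stimuli as covariates", and asks two questions: "Whether changes in responses to negative stimuli account for a significant proportion of changes in talkativeness" and "Whether the effect of drug on talkativeness is still significant after inclusion of the changes in responses to negative stimuli". The form in which the estimates enter is not stated. The exploratory mood analysis follows the same procedure.

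Session effects are handled by design only. Dose order is randomized (Design) and counterbalanced (Drug and Doses), and practice at Orientation is meant to reduce practice effects, not to remove them.

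**The concern.** Participants repeat the same picture, face and speech tasks four times, so drift from practice or habituation is plausible. For an average dose contrast, counterbalancing prevents bias, but the drift remains as unexplained within-person variation.

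Mediation has no such protection. Counterbalancing makes the difference in session position between a dose and placebo average zero across participants; it does not make it zero within each participant. If mediator and word count both drift, that difference enters both of a participant's changes. Negative responses falling while word count rises makes unrelated changes look linked in the hypothesised direction. If both rise or both fall, a true link is hidden. In the mood analysis the signs differ: anxiety and negative responses falling together would create a link.

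Mediation is part of Aim 3. The Objectives state that "the reduction in responses to negative emotional and social stimuli produced by CBD will result in greater talkativeness in a controlled social interaction", and the end of Significance predicts that "this effect will be mediated by the decreased responses to negative social and emotional stimuli measured in the previous aims".

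**Working it through.** **Inputs.** From the plan: four sessions, 50 recruited, 36 expected completers (Subjects). It gives no power, effect size, SD, alpha or trend size, so there is no planned figure to reproduce. Assumed: two-sided 5%; total SD 1; between-session correlation r = 0.5 or 0.7; linear trend b = 0.1, 0.2 or 0.3 SD per session; word-count dose effect 0.4 SD.

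**Step 1: dose contrast on word count.** For two of four sessions in random order, the mean squared difference in position is 10/3. Write v = 2(1−r) for the variance of a dose-minus-placebo change without trend, and q = (10/3)b² for what the trend adds. Omitting session multiplies the standard error by √(1 + q/v).

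Example, r = 0.5, b = 0.3: v = 1 and q = 0.30, so the factor is √1.30 = 1.140. SE = √(1/36) = 0.167 becomes 0.190. Power ≈ Φ(0.4/0.190 − 1.98) = Φ(0.12) = 55%.

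| r | b | SE factor | Power, formula | Power, simulated without session | Simulated with session |
|---|---|---|---|---|---|
| 0.5 | 0.1 | 1.017 | 65% | 64% | 65-66% |
| 0.5 | 0.2 | 1.065 | 61% | 61% | 65-66% |
| 0.5 | 0.3 | 1.140 | 55% | 55% | 65-66% |
| 0.7 | 0.1 | 1.027 | 85% | 85% | 86% |
| 0.7 | 0.2 | 1.106 | 79% | 81% | 86% |
| 0.7 | 0.3 | 1.225 | 71% | 73% | 86% |

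Simulated type I error without session is 3-5%, so it is not inflated.

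**Step 2: Drug × stimulus type.** A trend common to all stimulus types cancels. With a trend in negative stimuli only (and assumed variance components), simulated power without and with session terms is 65%, 63%, 59% against 67-68% for IAPS, and 68%, 66%, 62% against 68-69% for DEIT.

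**Step 3: false link.** With no true link and equal opposing trends, the two changes have correlation −q/(v + q). Example, r = 0.5, b = 0.3: −0.30/1.30 = −0.231. By Fisher's z with n = 36, atanh(0.231) × √33 = 1.35, so the two-sided rejection rate is Φ(1.35 − 1.96) + Φ(−1.35 − 1.96) = 27%.

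| r | b | Correlation | Formula | Simulated, 900mg-minus-placebo changes | Same, mediator trend halved | Simulated, mediator value per dose |
|---|---|---|---|---|---|---|
| 0.5 | 0.1 | −0.032 | 5% | 5% | 5% | 6% |
| 0.5 | 0.2 | −0.118 | 10% | 10% | 7% | 22% |
| 0.5 | 0.3 | −0.231 | 27% | 28% | 12% | 69% |
| 0.7 | 0.1 | −0.053 | 6% | 6% | 5% | 9% |
| 0.7 | 0.2 | −0.182 | 18% | 19% | 8% | 48% |
| 0.7 | 0.3 | −0.333 | 51% | 54% | 21% | 96% |

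Exactly balanced orders do not help: 5%, 10%, 28% (r = 0.5) and 5%, 18%, 56% (r = 0.7) for changes. One change per person crossed with Drug behaves like the change form (5%, 10%, 27% and 6%, 19%, 53%). A trend in one measure only gives 4.7-5.4%. One value per person as a main effect gives 4.7-5.7%. After session adjustment the rates are 4.5-5.6%.

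**Step 4: the full criterion.** Using changes, equal opposing trends and assumed 0.5 SD drug effects on both measures, the gate plus a false link in the hypothesised direction occurs in 3%, 8%, 19% (r = 0.5) or 5%, 17%, 46% (r = 0.7), against 2-3% after adjustment. False whole mediation occurs in 2%, 4%, 11% or 2%, 8%, 26%, against 1%.

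**Step 5: masking.** With a true correlation of 0.5 and equal trends working against it, the correlation becomes (0.5v − q)/(v + q). For r = 0.5, b = 0.3 this is 0.20/1.30 = 0.154. Simulated power falls from 89% to 81%, 50%, 13% (r = 0.5) or 73%, 26%, 3% (r = 0.7); after adjustment it is 88-89%.

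**The case against.** The large figures need large trends. A trend of 0.3 SD per session accumulates to 3 × 0.3 = 0.9 SD by session 4, more than twice the assumed dose effect, and 0.2 accumulates to 0.6 SD. No document supports such sizes, and at 0.1 the effects are small. This stands: every figure is conditional.

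The direction of drift is also uncertain. Practice on the DEIT would plausibly lower the intensity needed for identification, which the plan scores as more sensitivity to negative faces. With rising word count, that would hide the predicted link instead of creating it. Either way the mediation conclusion is affected.

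The text on per-participant estimates can be read as one value per person entered as a main effect, which is not affected. But that form cannot explain a within-person drug effect, and the plan asks whether changes account for changes.

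If the mediator is a negative-versus-neutral or negative-versus-happy contrast, a trend common to all types cancels. True; the mediator then does not drift and no false link arises from it.

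The gate limits harm. With no drug effect on word count, gate plus link is 1% or less; if the drug does not move the mediator, false whole mediation is about 1% or less. This also stands.

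The random Drug term is no remedy. In trial-level models it carries the session shift into the per-participant estimates. For word count, with one value per participant and dose, a by-subject Drug effect cannot be separated from residual error.

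**Conclusion.** The concern holds. The average dose contrasts are neither biased nor subject to inflated type I error, and the power loss on word count is slight at 0.1 SD per session, about 5 points at 0.2 and 11-14 at 0.3. The more serious consequence is for mediation: if both measures drift, the link can be false or missed, and counterbalancing does not prevent it. The size depends on assumed trends, on both measures drifting, and on how the estimates enter the model. A false link matters mainly when there is a drug effect on talkativeness; false whole mediation is rarer and also needs a drug effect on the mediator. The change should be made because a stated aim is exposed and the remedy is cheap. Confidence is medium, since the trend is unknown.

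**What to change.** - Word-count and mood models: add session (1-4, as a factor) as a fixed effect.
- IAPS, DEIT and ABT models: add session and session × stimulus type. A session main effect alone leaves the Drug × stimulus-type estimate unchanged.
- Mediation, including the mood analysis: state how the per-participant estimates enter. If one value per dose, the session factor in the outcome model is enough. If dose-minus-placebo changes, take both from session-adjusted models, or add the difference in session position as a covariate (this removes a linear trend only). If crossed with Drug, use session-adjusted estimates and the session factor in the outcome model.

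Only the analysis wording changes; session number is already known. The terms use 3 degrees of freedom for session, plus 6 for session × picture type or 9 for session × expression type. With no trend, power without and with them is 66.5% and 66.0% (word count, r = 0.5), 86.7% and 86.4% (r = 0.7), 66.8% and 66.8% (Drug × picture type), and 69.8% and 69.3% (Drug × expression type). For binomial gaze, in a stand-in logistic model, it is 56.3% and 54.7% (16 assumed trials per expression per session) or 55.6% and 54.3% (32 trials). The cost is about 0-2 points. For gaze, a trend of 0.1 logit per session gave no net gain, so the benefit there is the least certain.

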CBD will be obtained in pure form from GW Pharmaceuticals (GW Pharmaceuticals 2012). Our IND has been approved (IND 125302). CBD is currently in Phase II studies for several indications including MS neuropathic pain and spasticity, and a 1:1 ratio combined CBD and THC oral spray is approved in several countries in Europe and in Canada for MS related spasticity (GW Pharmaceuticals 2012). Preclinical toxicity data suggest a good safety margin between the clinical dose proposed and a toxic dose, and doses of up to 1500mg CBD per day in humans are reported to be well-tolerated (Zuardi et al. 2006). Adverse effects of CBD/THC combined products have been subject to greater study than CBD alone, and these include dizziness, nausea, fatigue, dry mouth, somnolence, anxiety, mood changes, transient hypotension or tachycardia, delusional ideas, disorientation, and hallucinations. Most of these effects are likely attributable to the THC present in these combinations (GW Pharmaceuticals 2012). Indeed, one review

of the safety and side-effects of CBD alone noted no adverse effects across several studies (Bergamaschi et al. 2011a). However, we will take precautions against these possible adverse effects in our CBD alone study. See “Risks” for complete safety precautions. CBD alone may produce mild sedation, but does not appear to produce subjective intoxication, marked negative effects on mood or changes in cardiovascular functioning (GW Pharmaceuticals 2012).

Study Tasks:

1. International Affective Picture System (IAPS) – (Lang et al. 1999) Participants will view standardized positive, negative and neutral pictures from the IAPS. The negative and positive images will be matched on degree of valence and arousal. We will record psychophysiological facial EMG responses during a 1s baseline recording period will precede each picture, and during the 6s presentation of each (see “Psychophysiological Measures”). An Evaluative Space Grid rating will follow each picture to collect subjective reactions (see “Subjective Measures”).

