Exploratory Analysis of Relationship to Mood: We will conduct similar within-subject mediational Mixed Linear Model analyses in R using lme4 on our primary outcomes of responses to negative stimuli, using subjective measures of anxiety (from the POMS), sedation (from the ARCI) and euphoria (from the POMS, ARCI and DEQ) as covariates. Following the procedure described above, we will determine whether the effects of the drug on responses to negative stimuli are partially or wholly mediated by its effects on subjective mood.

Human Subjects Information

Recruiting methods: We will place print ads in newspapers and on online job search sites such as craigslist.org, and flyer in the Chicago area. Healthy volunteers who respond to our ads are screened using our standard screening protocol for all studies in the Human Behavioral Psychopharmacology Laboratory, which is separately approved by the IRB under Protocol #13681B.

Obtaining consent: Written informed consent for the screening session only is obtained at the screening according to procedures outlined in Protocol #13681B. Written informed consent for the study procedures is obtained at the orientation session, after a verbal explanation of study procedures, check of comprehension, and an opportunity for the participant to ask any questions they may have. Consent is verbally re-verified at the beginning of each study session.

Risk to subjects:

1. Diagnostic procedures and questionnaires: Some of the questions asked during the screening may be considered sensitive information, including drug use history and psychiatric history. We have rigorous procedures in place to ensure confidentiality of data, including locked cabinets for confidential files, subject coding, secure computer systems, and rigorous training of personnel. Please see screening protocol #13681B for full information on steps taken to protect information gathered as part of the screening.

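### Mediation of talkativeness is judged through the significance of the total drug effect on word count, with no rule if that effect is not shown and no estimate of the indirect effect

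*Combined protocol and SAP*

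**What the plan says.** Aim 3 as set out under Significance predicts that CBD will increase talkativeness and that "this effect will be mediated by the decreased responses to negative social and emotional stimuli measured in the previous aims". The IST paragraph of Data Analysis gives the method. Word count is modelled on Drug at four levels. The mediation steps, attributed to a cited paper on within-subject designs, then begin: "we will first establish whether drug has the hypothesized effect on talkativeness". Next: "We will then include the per-participant estimates of the effect of drug on responses to negative stimuli as covariates". Two questions follow. Do the changes in response explain a significant share of the change in talkativeness, and is the drug effect still significant once they are included? Under whole mediation, "we would expect the effect of drug on talkativeness to no longer be" significant.

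The paragraph gives no rule for the case where the first step shows no effect. It states no alpha and plans no estimate, test or interval for the indirect effect itself.

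Exploratory Analysis of Relationship to Mood carries the procedure over: "Following the procedure described above, we will determine whether the effects of the drug on responses to negative stimuli" are partly or wholly mediated by mood.

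**The concern.** An indirect effect is the product of two paths: drug to mediator, and mediator to outcome. It can be real when the total effect is too small to detect, and the test of the total effect can be much weaker than the tests of the two paths. A procedure that starts from the total effect, and then reads mediation from that effect losing significance, has nothing to work with when it was not significant at the outset.

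The plan leaves that case open. Either the analyst stops, and a real pathway may go unreported, or the analyst decides after seeing the result whether to go on. Mediation is a stated prediction of the study, and the Significance section ties its treatment argument to whether altered emotional responses contribute to social behaviour. The answer should not depend on an unstated choice.

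**Working it through.** **Inputs.** From the documents: 36 expected completers (Subjects), a within-subject design with four dose levels (Design), and total word count as outcome (IST). The documents give no alpha, power, SD or effect size for word count, so there is no power figure to reproduce. Assumed: two-sided 5% tests and a range of standardised effects.

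**Step 1: power of the total-effect test.** For one CBD dose against placebo, with total effect d in SDs of the paired difference, the test is a paired t with 35 df and noncentrality d × √36 = 6d.

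| d | Power |
|---|---|
| 0.10 | 9% |
| 0.20 | 21–22% |
| 0.30 | 42% |
| 0.336 | 50% |
| 0.40 | 65% |
| 0.48 | 80% |
| 0.50 | 83% |

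The plan models four doses, so other forms of the test were checked. If the effect rises linearly to d at 900 mg, the 3-df F test (3 and 105 df) has 31% power at d = 0.3 and 53% at 0.4. A linear trend test has 47% and 71%. The break-even point is therefore about 0.3 to 0.4 whichever form is used.

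**Step 2: cost of using it as a precondition.** Simulation of 36 paired differences, 20,000 runs per row:

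- mediator change M = a + u, with Var(u) = 1
- word-count change Y = c′ + bM + e, with Var(e) = 1 − b², so that Y also has unit variance
- total effect = c′ + ab; for example, 0 + (−0.6)(−0.5) = 0.30

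Mediation counts as detected when paths a and b are both significant in the predicted direction. The last column also requires a significant total effect.

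| a | b | c′ | Total | Both paths | Both paths and total effect |
|---|---|---|---|---|---|
| −0.6 | −0.5 | 0 | 0.30 | 83% | 36% |
| −0.5 | −0.4 | 0 | 0.20 | 58% | 14% |
| −0.8 | −0.7 | 0 | 0.56 | 99.5% | 90% |
| −0.6 | −0.5 | +0.2 | 0.50 | 84% | 71% |
| −0.6 | −0.5 | +0.3 | 0.60 | 84% | 79% |
| −0.6 | −0.5 | −0.1 | 0.20 | 83% | 18% |
| −0.6 | −0.5 | −0.2 | 0.10 | 84% | 8% |

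Fixing the residual SD at 1 instead changes the first row to 75% against 27%, so the pattern does not depend on the scaling.

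**Step 3: false positives without the precondition.** With either path set to zero and no shared cause, the two-path test is positive in about 2% of runs. The mediator is not randomised, however. With a = −0.6, true b = 0, no total effect, and a shared cause giving a correlation of −0.3 between the two changes, it is positive in about 40% of runs (20% at −0.2, 65% at −0.4). Requiring a total effect as well cuts this to about 1–2%. If the drug also has a real direct effect of 0.5, the requirement still lets through about 34% at a correlation of −0.3.

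**The case against.** The strongest reply is that the text sets an order and not a stop. It says that the effect will be looked for first and that the covariates will then be added; no conditional appears. On that reading both paths are tested anyway. The drug effect on negative-stimulus response has its own unconditional analyses under IAPS, DEIT and ABT, and its link with talkativeness is the first of the two IST questions. This stands as a reading. It does not supply an indirect-effect estimate, and the second question still has no meaning if the drug effect was never significant.

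Next, Aim 3 predicts an increase in talkativeness and then explains it, so without an increase the hypothesis as worded has failed. That stands, and it is why the total-effect test should be kept.

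Third, the shared-cause result in step 3 shows that the precondition gives some protection. That also stands when there is no total effect. The protection is largely lost once the drug has a real direct effect, so the result calls for cautious causal wording and does not justify keeping the precondition.

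Fourth, the mood analysis is exploratory and asks what accounts for observed effects, so needing an effect first is more natural there. This lowers the stakes for that analysis.

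A reader might also infer that sedation would cancel a real pathway, since Drug and Doses notes that "CBD alone may produce mild sedation". No section says that sedation lowers word count. The two rows with negative c′ are therefore assumptions only, and the point does not need them.

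**Conclusion.** The point holds as a gap in the mediation method. The plan treats a total drug effect as the first criterion, judges mediation by that effect losing significance, leaves the other case undefined, and does not estimate the quantity of interest. If the first step is applied as a precondition with 36 completers, it is more likely than not to fail when the total effect is below about 0.34 SD of the paired difference. Detection of a real pathway can then fall by more than half (83% to 36% in the reference case).

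A reader might go further and infer that mediation will be examined only after a significant total effect, and will usually be abandoned. The documents do not support that: they contain no stopping rule and no effect size. The loss is modest with large paths (99.5% to 90%) or a same-direction direct effect (84% to 71%). All these figures rest on assumed effects, a two-sided 5% level and, in the simulation, a single dose contrast.

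**What to change.** In the IST paragraph, keep the test of the total drug effect on word count as a hypothesis in its own right. Add that the indirect effect through within-participant change in negative-stimulus response will be estimated with a confidence interval whatever the total-effect result, and that total, direct and indirect effects will be reported together. State the alpha and the dose contrast used. Apply the same rule to the exploratory mood analyses.

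Add one caveat: because the mediator is not randomised, an indirect effect without a total effect may reflect a shared cause. It should be reported as an association and not as evidence that CBD increased talkativeness.

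The cost is a few sentences of analysis text and some extra estimates from data already being collected. The downside is that an indirect effect may be reported without a total effect, which the caveat covers.
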